The current proposal will build on our pilot study and utilize a double-blind, mixed-model design with a between-groups factor of dose (pioglitazone vs. placebo) and a within-subjects factor of time. Eligible participants will consist of treatment-seeking individuals with AUD who score high on screening measures of stress/anxiety and stress-related drinking. Study medication (pioglitazone or placebo) will be administered for 8 weeks. Relapse risk outcomes will be assessed using both a human laboratory paradigm of stress reactivity and stress-induced craving (Specific Aim 1) and real-life measures of stress/anxiety, craving, and alcohol consumption (Specific Aim 2).

Strengths of the current proposal include: 1) targeting individuals with elevated stress/anxiety and AUD; 2) biological assessment of stress reactivity (heart rate, blood pressure, salivary cortisol); 3) a multi-dimensional assessment of alcohol craving incorporating relatively novel behavioral economic measures (i.e., alcohol demand, delay discounting); and 4) inclusion of powerful Bayesian statistical tools that are well suited for smaller samples, such as the current proposal.

We propose the following Specific Aims:

Specific Aim 1: To examine the effects of pioglitazone on stress-induced relapse risk in a laboratory model.

Hypothesis 1a: Participants receiving pioglitazone will show decreased stress reactivity (heart rate, blood pressure, salivary cortisol) compared to those receiving placebo.

Hypothesis 1b: Participants receiving pioglitazone will show decreased alcohol craving (subjective, alcohol demand) compared to those receiving placebo.

Specific Aim 2: To examine the effects of pioglitazone on drinking, stress/anxiety, and alcohol craving in the natural environment.

Hypothesis 2a: Participants receiving pioglitazone will show greater reductions in weekly psychometric measures of stress/anxiety compared to those receiving placebo.

Hypothesis 2b: Participants receiving pioglitazone will show greater reductions in weekly psychometric measures of alcohol craving compared to those receiving placebo.

Hypothesis 2c: Participants receiving pioglitazone will show greater reductions in past week alcohol use (heavy drinking days, average drinks/day) compared to those receiving placebo.

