Figure 1. Changes in stress reactivity (left panel) and weekly measures of stress/anxiety, alcohol craving, depressive symptoms, and alcohol consumption (right panel).

Overall Study Design. To accomplish the project aims, we will utilize a double-blind, mixed-model design with a between-groups factor of dose (pioglitazone vs. placebo) and a within-subjects factor of time. We will utilize urn-randomization based on gender and severity of alcohol use (AUDIT). A summary of the study timeline, procedures, and assessments is shown in **Table 1** below.

Table 1. Outline of Study Timeline, Procedures, and Assessments

Study Week	0	1	2	3	4	5	6	7	8
Procedures and Assessments	IRB	NU	BE						
Consent and Baseline Screening	IRB	APP	OVAL						

SCID, ASI, KMSK, TLFB, CIWAA, AUDIT	X								
Receive Study Medication (Pioglitazone or Placebo)	X	X	X	X	X	X	X	X	X
Assess Medication Compliance and Adverse Events		X	X	X	X	X	X	X	X
Brief Counseling	X	X	X	X	X	X	X	X	X
Human Laboratory Assessments (Specific Aim 1)									
Stress-Reactivity Assessment (Salivary Cortisol, HR, BP, self-report)	X				X				X
Alcohol craving (self-report, brief alcohol demand)	X				X				X
Weekly Assessments (Specific Aim 2)									
Alcohol Use and Craving (TLFB, BrAC, ETG, PACS, DMQ-R)	X	X	X	X	X	X	X	X	X
Stress and Anxiety (HAM-A, PSS, PCL-5)	X	X	X	X	X	X	X	X	X
Delay Discounting, Alcohol Demand (purchasing task)	X				X		X	X	X

SCID - Structured Clinical Interview for DSM-5, **ASI** - Addiction Severity Index⁶⁵; **KMSK** - Kreek-McHugh-Schluger-Kellogg scale⁶⁶; **TLFB** - Timeline Followback⁶⁷; **CIWAA** - Clinical Institute Withdrawal Assessment for Alcohol⁶⁸; **AUDIT** – Alcohol Use Identification Test⁶⁹; **BrAC** – Breath Alcohol Concentration; **ETG** – Ethyl Glucuronide; **PACS** – Pennsylvania Alcohol Craving Scale⁷⁰; **DMQ-R** – Drinking Motives Questionnaire Revised^{1,2}. **HR** – Heart Rate; **BP** – Blood Pressure; **HAM-A** – Hamilton Anxiety Rating Scale⁷¹; **PSS** – Perceived Stress Scale⁷²; **PCL-5** - PTSD Checklist for DSM-5⁷³.

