Inferential Paradigm Following recommendations in the literature¹⁰⁶⁻¹⁰⁸, analyses will utilize parallel frequentist and Bayesian statistical inference. Frequentist results yield the probability of the data (or data more extreme), given the null hypothesis, whereas Bayesian results directly yield the probability of an alternative hypothesis¹⁰⁹. If possible, Bayesian analyses will incorporate informative priors as they develop in the literature; otherwise, weakly informative priors will be incorporated as a default. Sensitivity analyses using optimistic and pessimistic, skeptical priors will evaluate prior assumptions¹¹⁰. Assessing the convergence of Bayesian analyses on the posterior distributions via Monte-Carlo Markov chain (MCMC) will use diagnostic evidence including effective sample size and scale reduction factors. Evaluation of posterior distributions will permit statements regarding the probability that effects of varying magnitudes exist, given the data. Statistical analyses will use the most up-to-date stable release version of the R statistical computing environment¹¹¹ using packages rstan¹¹¹ and brms¹¹².

Statistical Modeling Analyses will primarily use generalized linear modeling (GLM). Continuous, count, and dichotomous outcome variables will utilize normal, Poisson/negative binomial, and binomial distribution families respectively, with identity, log, and logit link functions as appropriate. Evaluation of distributional assumptions will use residual plots, formal statistical tests, and posterior predictive checking. Violations of assumptions will be addressed via transformation, robust estimation, stratification, and/or coefficient scaling where appropriate.

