HAM-A) compared to those receiving placebo. **Hypothesis 2b:** Participants receiving pioglitazone will show greater reductions in weekly psychometric measures of alcohol craving (primary measures: PACS) compared to those receiving placebo. **Hypothesis 2c:** Participants receiving pioglitazone will show greater reductions in past week alcohol use (primary measures: heavy drinking days as defined by >3 drinks/occasion for women and >4 drinks/occasion for men, average drinks/day) compared to those receiving placebo.

For all hypotheses, GLMM will model primary outcome measures as a function of the main effects and interaction between treatment and time.

Sample Size and Power Considerations

Frequentist Analyses. Power for **Specific Aim 1** is based on the rate at which we may detect the three-way interaction between time, treatment, and CPT measurement point for a given measure of stress reactivity (transformed for normality) across $k = 1000$ Monte Carlo simulations (executed via SAS 9.4). Calculations assume the following conditions: $\alpha = 0.05$, an autocorrelation of $r = 0.50$ between consecutive observations (with a decay of $r = -0.10$ for subsequent observations), and a small correlation of $r = 0.05$ for observations occurring at the same time point across groups. Based on these assumptions, the different sample sizes (pragmatic and pessimistic) stipulated in **Table 3** each provide power to detect small-to-moderate effect sizes (treatment group differences expressed as Cohen's D, with effects unfolding in linear fashion over time). Power for **Specific Aim 2** is based on evaluating reductions in drinks per week. Estimates are derived using G*Power 3.1.9.2. Assuming $\alpha = 0.05$ (two-tailed) and an average baseline of drinks/week across participants (calculated as an average from 14 and 7 drinks/week for a 3:1 ratio of males to females, respectively), the different sample sizes (pragmatic and pessimistic) stipulated in **Table 3** each provide power to detect varying decreases in alcohol consumption.

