Bayesian Analyses. The Bayesian analyses in the current proposal will provide probabilistic estimates of effects for all hypotheses irrespective of statistical power. Moreover, the MCMC approaches utilized in Bayesian analyses do not rely on large sample size assumptions. Bayesian analyses will focus on posterior probabilities ≥ 0.75 (equivalent to a Bayes factor = 0.33 or 3.0) that parameter estimates are greater or less than zero to emphasize the value in discerning model effects.

Table 3. Power estimates for Aims 1 and 2 given different sample and effect sizes.

N (N/group)	SA1: Group Difference (Cohen's D)			SA2: % Decreased Consumption		
	D = 0.50	D = 0.40	D = 0.30	-12.0%	-11.0%	-10.0%
50 (25/25)	100.0%	97.8%	84.6%	97.8%	95.2%	90.8%
40 (20/20)	99.8%	95.0%	71.8%	88.6%	82.5%	74.6%

Cohen's D for observed within-subject effects sizes from our Preliminary Data are as follows: HR (0.8), BP (systolic - 0.5, diastolic - 1.6), cortisol (0.13), PSS (2.1), HAM-A (1.3), BDI (1.2), PACS (1.5), Drinks/week (1.3), Heavy drinking (0.8). Note that Table 3 effect sizes represent between group differences unfolding over time.

STUDY TIMELINE

The time frame illustrated in **Table 4** below is based on conservative estimates. We will continuously monitor our procedures and implement measure to enhance progress as indicated. Our goal is to enroll 60 subjects to achieve 25 completers/group. However, we will continue to enroll subjects based on available resources and subject attrition. Pre-award preparations following pre-award requests (just-in-time (JIT)) will include submitting an initial IRB protocol. Startup will include hiring and training of study staff. Over the course of the study, preliminary and final results will be presented at appropriate scientific conferences (e.g., Research Society on Alcoholism, College on Problems of Drug Dependence, Research Society on Alcoholism, etc.).

Table 4. Study Timeline.

	Year 1													Year 2											
	Month													Month											
	1	2	3	4	5	6	7	8	9	10	11	12	1	2	3	4	5	6	7	8	9	10	11	12	
Pre-award prep																									
	Startup																								
				Phone screens: 250												IRB	NUL	BE	: H	C-N	S-1	-092			
				IRB APPROVAL												DAT	: 10	11/2							

			Intake evaluations: 100											
			Enrollment and randomization: 60 (~3-4 subjects/month)											
			Completion of protocol (~3-4 subjects/month)											

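### The two Aim 2 rows of Table 3 cannot both follow from the inputs the protocol states: power falls further from N = 50 to N = 40 than the change in sample size allows

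*Combined protocol and SAP*

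**What the plan says.** All references are to the combined protocol and SAP.

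- **Sample Size and Power Considerations, Frequentist Analyses.** Aim 2 power "is based on evaluating reductions in drinks per week. Estimates are derived using G*Power 3.1.9.2". Alpha is 0.05, two-tailed. The baseline is "calculated as an average from 14 and 7 drinks/week for a 3:1 ratio of males to females, respectively". The results are attributed to "the different sample sizes (pragmatic and pessimistic) stipulated in" Table 3; nothing else is said to vary between the rows. The G*Power procedure is not named, and no exposure time, SD, dispersion or within-person correlation is given for Aim 2.
- **Table 3, Aim 2 columns.** For decreases of 12/11/10%, power is 97.8/95.2/90.8% at 50 (25/25) and 88.6/82.5/74.6% at 40 (20/20). The text below the table adds: "Note that Table 3 effect sizes represent between group differences unfolding over time".
- **Specific Analyses, Aim 2.** "For all hypotheses, GLMM will model primary outcome measures as a function of the main effects and interaction between treatment and time".
- **Statistical Modeling.** Continuous, count and dichotomous "outcome variables will utilize normal, Poisson/negative binomial, and binomial distribution families respectively".
- **Specific Aims.** "Study medication (pioglitazone or placebo) will be administered for 8 weeks".

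**The concern.** If two rows of a power table share the test, alpha, baseline and effect, and differ only in the number of participants, one row fixes the other. Whatever the unstated SD, exposure or dispersion may be, it cancels in the comparison. The printed drop from 50 to 40 completers is 9.2/12.7/16.2 percentage points, which looks too large for losing one fifth of the sample.

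Table 3 is the only power calculation for Aim 2, and its primary outcomes are to be tested at alpha 0.05. As printed, a reader cannot tell whether the lower row is too low, the upper row is too high, or the two were run on different assumptions. The upper row is the completer target, so the doubt reaches the figure on which the trial relies.

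**Working it through.** **Inputs.** Alpha 0.05 two-sided (z = 1.96); baseline (3 × 14 + 1 × 7)/4 = 12.25 drinks/week; rate ratios (RR) 0.88, 0.89 and 0.90; 25 or 20 per group. All are from Sample Size and Power Considerations and Table 3.

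**Step 1. Try to reproduce the printed figures.** No procedure is named, so this needs an assumption. Take a Poisson rate comparison in Wald form, with n per group and t weeks of exposure:

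power = Φ( |ln RR| / √[(1 + 1/RR)/(n × 12.25 × t)] − 1.96 )

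With t = 8, the planned treatment period, this gives 99.1/97.7/94.8% at N = 50 and 97.2/94.3/89.4% at N = 40. Neither row is reproduced. Solving for t, the N = 50 row is matched at about 6.7 weeks and the N = 40 row at about 5.35 weeks. No common exposure fits both: the best, about 5.9 weeks, misses by up to 4.0 points. These exposures are back-solved; the documents do not report them.

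**Step 2. Compare the rows without assuming exposure, SD or dispersion.** For a two-sided test on one degree of freedom, the noncentrality is δ = z(power) + 1.96, and δ² is proportional to N.

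| Decrease | δ at N = 50 | δ at N = 40 | Ratio of δ² | Expected |
|---|---|---|---|---|
| 12% | 2.014 + 1.960 = 3.974 | 1.206 + 1.960 = 3.165 | 1.576 | 1.25 |
| 11% | 1.665 + 1.960 = 3.625 | 0.935 + 1.960 = 2.895 | 1.568 | 1.25 |
| 10% | 1.329 + 1.960 = 3.289 | 0.662 + 1.960 = 2.622 | 1.573 | 1.25 |

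Rounding of the printed powers to 0.1 point allows ratios of only 1.56 to 1.59.

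**Step 3. Carry each row to the other sample size.**

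- N = 50 to N = 40: multiply δ by √0.8 = 0.894, giving 3.555/3.242/2.941 and power 94.5/90.0/83.7%. The printed values are lower by 5.9/7.5/9.1 points. The implied loss from 50 to 40 is 3.3/5.2/7.1 points.
- N = 40 to N = 50: multiply δ by √1.25 = 1.118, giving 3.539/3.236/2.931 and power 94.3/89.9/83.4%. The printed values are higher by 3.5/5.3/7.4 points.

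On the same basis, the lower row behaves like N = 50/1.57, about 32.

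**Step 4. Other tests.** A two-sample t-test fitted to the N = 50 row gives 94.2/89.7/83.3% at N = 40. One-sided alpha in both rows raises the ratio to about 1.65. A mixed setting (N = 50 one-sided, N = 40 two-sided, about 5.4 weeks) comes within 0.6 points of all six cells, but contradicts the stated two-tailed alpha.

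**Step 5. Conditional check on dispersion.** Assume an unadjusted Poisson comparison of 8-week means with between-person coefficient of variation CV:

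SE² = (1/n) × [ (1 + 1/RR)/(8 × 12.25) + 2CV² ]

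For the 12% decrease at N = 50, the required SE is 0.1278/3.974 = 0.03217. Then 25 × SE² = 0.02587, the Poisson part is 2.1364/98 = 0.02180, and CV = √(0.00407/2) = 0.045. At N = 40 the same steps give 0.073.

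The true CV is not in the documents. As an assumed range, unadjusted power for a 12% decrease at N = 50 is about 88% at CV 0.1, 52% at 0.2 and 14% at 0.5. Simulated baseline-adjusted power at those CVs is about 88/61/36% with one baseline week and 91/80/70% with four, assuming a stable person effect and a uniform response.

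**The case against.** **The consequence of the mismatch is limited.** If the N = 50 row is right, the N = 40 row merely understates power. If the N = 40 row is right, the target of 50 completers still has 94.3/89.9/83.4%. Either way it stays above 80% in every column. The Innovation section also ties the small size to the funding mechanism, and the Bayesian results are offered irrespective of power. All of this stands and argues for a table correction rather than a redesign. It does not make the rows agree.

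**The implied values depend on the test.** With a nine-occasion group-by-time F-test, the N = 50 row carries to about 93.4/88.4/81.6% (univariate) or 91.9/86.5/79.3% (multivariate) at N = 40. The figures in Step 3 should therefore be read as holding for one degree of freedom. Even so, neither F-test version comes down to the printed 88.6/82.5/74.6%.

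**Three stronger readings are tempting, and the documents do not support them.**

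- A reader might infer that over-dispersion leaves Aim 2 underpowered. The CVs of 0.045 and 0.073 need an assumed Poisson model, 8 weeks of exposure and an unadjusted comparison. The plan instead has a treatment-by-time mixed model, permits negative binomial models, and says "We will utilize urn-randomization based on gender and severity of alcohol use (AUDIT"). A mixed model can absorb stable differences between people, and adjustment for gender would remove the variance from the 14/7 mix.
- A reader might infer that restated power must fall. Pure Poisson at 8 weeks gives higher power than printed (Step 1), so the direction is open.
- A reader might take the back-solved exposures, or the mixed sidedness, as what was actually run. They are reconstructions only.

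**Conclusion.** The row mismatch holds. With one two-tailed alpha, one baseline and only sample size differing, the two Aim 2 rows cannot both be right: the squared noncentrality ratio is about 1.57 against 1.25, and rounding does not explain the gap. For a one-degree-of-freedom test, either the N = 40 row is 5.9 to 9.1 points too low, or the N = 50 row is 3.5 to 7.4 points too high, or an unstated input differs between them. The documents do not show which. This conclusion needs no assumption about exposure, SD or dispersion beyond their being common to both rows.

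The dispersion point is separate and conditional. The text states no exposure, dispersion or within-person correlation for Aim 2, and under the Step 5 assumptions the printed powers leave little room for between-person variation (CV about 0.05 to 0.07). The effect on the planned treatment-by-time model is not established.

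This should be corrected, but it does not call the sample size or the analysis into question.

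**What to change.** - Rerun both Aim 2 rows with the same test, sidedness and exposure, as a between-group comparison over time that matches the planned model.
- State the G*Power procedure (or simulation), the exposure in weeks per person, the dispersion and the within-person correlation, with a range for dispersion.
- Restate the power for each assumed dispersion, or the percent reduction detectable with 80% power.
- If the pessimistic row carries a further assumption, such as shorter follow-up, state it beside the row.

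The cost is one recalculation and an edit to Table 3 and its paragraph. The restated power may go up or down, depending on the inputs chosen. No change to sample size or analysis is needed.
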